3.2 Informed Consent, Participant Surveys, and Educational Intervention

As patients wait to have the mammogram, they will be screened for eligibility. Following completion of the mammogram, patients will return to the changing room and put on their clothing. After exiting the changing room in the Lynn Sage Comprehensive Breast Center of Northwestern Medicine/Prentice Women's Hospital and as they are preparing to leave, a research assistant (RA) will interview potential participants to acquire a randomly selected convenience sample of eligible participants (n=800). Participants will be invited to complete a survey that will assess knowledge of melanoma and the risk of developing a melanoma. They will be provided with a consent form and the research study will be discussed, questions will be invited and then they will be asked to sign a consent form and to fill out a registration form containing contact information. (see attached)

The complete survey includes general demographic items such as age, education, household income, race and ethnicity. The survey questions are as follows:

1. During your visit for mammography, did you notice any information about checking your skin for melanoma?

Yes No

2. Did you think this applied to you?

Yes No

3. If no, why not? (open ended)

4. If yes, why? (open ended)

5. Did you check your skin? (If no, please proceed to question #7)

Yes No

6. If yes, did you notice any concerning moles?

Yes No

7. If no, will you consider checking your skin in the future?

Yes No

8. If you found any concerning moles, did you make an appointment to see a dermatologist?

Yes No

The RA will record the responses.

3.3 Research procedures and activities

Follow-Up

1 week after the mammogram, RA will contact participants in group 1 via their preferred method to remind them to perform SSE and schedule a dermatologist appointment if they find a concerning mole. (see attached telephone script)

1 month after the mammogram, the RA will call participants in group 1 and administer a survey to see if they checked their skin and/or made an appointment with a dermatologist.

Effect of SSE education delivered during the mammography experience.

(see attached telephone script) An anonymous REDCap survey may be used in place of the telephone call, depending on participant's preferred method of contact preference.

The survey questions are as follows:

1. Did you read the brochure?
 Yes No
2. Did you check your skin? (If no, please proceed to question #4)
 Yes No
3. If yes, did you notice any concerning moles?
 Yes No
4. If no, will you consider checking your skin in the future?
 Yes No
5. If you found any concerning moles, did you make an appointment to see a dermatologist?
 Yes No

If no, do you intend to do so in the near future?

6. Did you share the brochure with anyone else?
 Yes No
7. If yes, who did you share it with:
 - a) A relative: son, daughter, father, mother, sister, brother
 - b) A friend : woman, man
 - c) Someone I work with: woman, man

REDCap Survey

3 months after the mammogram, an anonymous REDCap survey will be emailed to each woman enrolled in both groups. If participants do not complete the REDCap survey in 2 weeks, they will be called and surveyed via telephone. The following items with relevance to the research:

1. Do you have a history of sunburn? Yes/No
2. Do you have a history of more than 10 indoor tanning sessions? Yes/No
3. Do you have a personal or family history of melanoma? Yes/No
4. Have you ever performed a skin self-examination prior to your most recent mammogram? Yes/No

Effect of SSE education delivered during the mammography experience.

5. Did you perform a skin self-examination after your most recent mammogram?
Yes/No
If no, then go to item 8.
6. Did you find a concerning mole? Yes/No
7. If you found a concerning mole, did you make an appointment to see a dermatologist? Yes/No
8. If you did not perform a skin self-examination, did you still make a follow-up appointment to see a dermatologist for a skin examination? Yes/No
9. Have you had an appointment with a dermatologist yet? Yes/No
10. If you found a concerning mole and saw a dermatologist, was the concerning mole biopsied? Yes/No
 - a. If yes, was the biopsy done at Northwestern? Yes/No
 - b. If No, were you told by your dermatologist that the skin biopsy was melanoma? Yes/No
11. If you saw a dermatologist, were any other concerning moles biopsied? Yes/No

EMR review

If a woman responds yes to item 9 indicating that they made an appointment with a dermatologist, then the EMR will be checked to ascertain the findings of the dermatologist. The pathology report of biopsied mole(s) will be reviewed and added to the deidentified database.

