A research assistant will be present at the mammography center to collect consent, telephone numbers, iPhone model information, and email addresses to have women sign onto REDCap to complete a survey. A telephone survey will be administered to each woman enrolled in the study in both groups (N=800) one month after the mammogram asking if she performed a SSE at home and whether a follow-up with dermatology was made. An anonymous REDCap survey may be used in place of the telephone call, depending on participant's preferred method of contact preference. Then, three months after the screening mammogram, an anonymous <2 minute REDCap survey will be sent via email to each woman enrolled in both groups to ascertain the number of women who identified that they were at increased risk for melanoma (history of sunburn, history of indoor tanning >10+sessions, family or personal history of skin cancer), performed a SSE at home, found a concerning lesion, made a follow-up appointment with a dermatologist, and had any concerning lesions biopsied. If participants do not complete the REDCap survey in 2 weeks, they will be called and surveyed via telephone. We anticipate a 20% attrition rate (Fig 3). Participants will be offered a \$10 Amazon gift card in appreciation of completing the one month survey and an additional \$10 for completing of a second REDCap survey three months after the mammogram visit.

Effect of SSE education delivered during the mammography experience.

Fig 3. CONSORT diagram for two arms of study

Effect of SSE education delivered during the mammography experience.

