12.0 Financial Compensation

12.1 N/A. Participants will receive a \$10 Amazon gift card for participation in the second survey (telephone call/REDCap one month after mammogram visit) and an additional \$10 Amazon gift card for completing a third survey (REDCap) three months after the mammogram.

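### REDCap surveys labelled anonymous cannot feed the EMR review or the correspondence rate; item 11 and the EMR trigger also need correcting

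*Combined protocol and SAP*

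**What the plan says.** On the surveys, Section 3.3 (Research procedures and activities, REDCap Survey) says: "3 months after the mammogram, an anonymous REDCap survey will be emailed to each woman enrolled in both groups". Section 3.1 (Study Design, Phase 2) repeats the label for the three-month survey and adds, for the one-month contact: "An anonymous REDCap survey may be used in place of the telephone call". The same section collects "email addresses to have women sign onto REDCap to complete a survey".

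On follow-up of the surveys, Section 3.3 says: "If participants do not complete the REDCap survey in 2 weeks, they will be called and surveyed via telephone". Section 12.0 promises an "Amazon gift card for completing a third survey (REDCap) three months after the mammogram".

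On linkage, the EMR review paragraph of Section 3.3 has the EMR checked when a woman answers yes to item 9, and has the pathology report added to a deidentified database. Section 3.4 (Measures) plans a correspondence rate between the woman's assessment at SSE and the dermatologist's. Section 15.0 (item 5) has all data recorded by study number. Section 14.0 lists SSE performance, biopsy and diagnoses as primary outcomes.

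On the items themselves, item 5 of the three-month survey tells a woman who did no SSE: "If no, then go to item 8". Item 9 asks: "Have you had an appointment with a dermatologist yet". Item 10 covers a concerning mole that she found, and has sub-items on biopsy location and on being told of melanoma. Item 11 covers other biopsied moles and has no sub-items.

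**The concern.** An anonymous return cannot be traced to a woman, so nobody could tell whose record to open after a yes to item 9, or whose dermatology finding to set against which self-assessment. The plan cannot both keep the label and carry out the EMR review.

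Two things are at stake: diagnosis, one of the three primary outcomes in Section 14.0, and the correspondence rate in Section 3.4. The label also matters to participants. If women are told that a survey is anonymous and their answers are then used to open their records, the study does something other than what it told them.

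Two smaller problems would remain if the surveys were coded. Some biopsies could be reported with no source for the diagnosis, and the sections that govern EMR access do not describe the same trigger or the same scope.

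**Working it through.** The plan states no figure on this point, so there is nothing to reproduce. The check compares the sections.

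**1. What each procedure needs to know**

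- Calls to non-completers and gift cards (Sections 3.1, 3.3, 12.0): who completed. Completion status can be kept apart from the answers, so these are secondary evidence only.
- EMR review (Section 3.3): who answered yes to item 9, and which database entry receives the pathology report.
- Correspondence rate (Section 3.4): a woman's own answer and the dermatologist's finding for the same woman.
- Comparison of the two groups (Sections 3.4, 14.0): arm only. None of the 11 three-month items records arm, so even this needs at least a separate link per group.

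The second and third conflict with anonymity. No section describes how a REDCap response is joined to a study number.

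**2. What an anonymous return could still supply, if arm is known**

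- SSE performance: yes, item 5.
- Dermatology visit: yes, item 9.
- Biopsy: yes by self-report, items 10 and 11.
- Diagnosis, biopsy at Northwestern: no. Item 10b follows a 'no' to item 10a, so on its natural reading it is asked only about biopsies elsewhere. The EMR is then the only source.
- Diagnosis, biopsy elsewhere under item 10: self-reported melanoma, yes or no.
- Correspondence rate: no.

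**3. Size**

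Let R be the number answering at three months, s the share of them answering by REDCap, and y the item 9 yes rate, assumed equal in both modes.

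- Charts called for = R × y
- Charts that cannot be opened from the returns = R × s × y
- Share lost = (R × s × y) / (R × y) = s

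The documents give 800 enrolled and 20% anticipated attrition, so 800 × (1 − 0.20) = 640 would remain, but they do not tie that attrition to the three-month survey. They give neither s nor y. The result therefore stays a share, not a count.

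**4. Diagnosis sources with coded surveys**

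Assume that the EMR holds only Northwestern records, that all of a woman's biopsies were at one site, and that item 10 applies only to a mole found at SSE. Five answer patterns contain at least one biopsy:

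| Pattern | Biopsy reported in | Diagnosis source if biopsied elsewhere |
|---|---|---|
| No SSE | item 11 | none |
| SSE, no mole found | item 11 | none |
| SSE, mole found but not biopsied | item 11 | none |
| SSE, found mole biopsied only | item 10 | self-reported melanoma, yes/no |
| SSE, found mole and another biopsied | items 10 and 11 | self-report for the found mole; none for the other |

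Two sites give 5 × 2 = 10 patterns. In the 5 at Northwestern, pathology is reachable once the response is linked. In 4 of the 5 elsewhere, a mole reported in item 11 has no diagnosis source. These are counts of patterns, not of women.

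**5. EMR trigger and scope**

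- Section 3.1 (Inclusion Criteria): access to visits with a dermatologist or primary care physician about a concerning lesion, and to the biopsy result.
- Section 3.3 (EMR review): any yes to item 9, which the paragraph describes as having made an appointment. Item 9 asks whether she has had one; items 7 and 8 ask about making one. A woman who has booked but not yet attended meets the description and fails the item. A woman who had a screening examination with no concerning mole passes the item.
- Section 3.4: a yes to dermatology follow-up, with no survey or item named.
- Section 13.2: dermatologist visits for a concerning mole only.

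**The case against.** The strongest reply is that 'anonymous' is one loose word. Women consent to EMR access, give email addresses for signing onto REDCap, and have their data recorded by study number, with a master code list mentioned in Section 15.0. Read as a whole, the document describes coded data, and details of the link may sit in the consent and registration forms, which are not in the text reviewed. This largely stands. It makes the problem one of wording and procedure, and it lowers the severity. It does not remove the contradiction: staff could still set up an anonymous REDCap link, or women could be told something that the EMR review then breaks.

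A second reply is that the stakes are limited. The aims, and the two chi-square comparisons in Section 3.4 (performed SSE, saw a dermatologist), rest on survey answers, and diagnoses are tested only under Section 14.0. That also stands. The loss is confined to diagnosis and the correspondence rate.

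A third is that the item 11 gap is narrow. It depends on the EMR holding only Northwestern records, and the documents do not say how many biopsies are expected elsewhere. The gap is real under that assumption, but its size is unknown.

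**Conclusion.** The contradiction holds and should be fixed before the surveys are sent. Followed as labelled, the REDCap returns could supply neither Northwestern diagnoses nor the correspondence rate. The share of charts affected equals the REDCap share of responders if the item 9 yes rate does not differ by mode. The item 11 gap holds if the EMR covers Northwestern only. The misdescription of item 9 and the differing EMR triggers and scopes need no assumption.

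A reader might infer more than the documents support:

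- *That a given number of charts would be lost.* Any count needs a REDCap share and a yes rate that the documents do not give.
- *That only women telephoned after failing to complete REDCap could be linked at three months.* Section 3.1 (Study Design, Phase 1) offers that survey by REDCap or telephone without restricting the telephone to non-completers.
- *That EMR ascertainment would differ by arm because Section 3.3 gives the one-month call to group 1 only.* Section 3.1 (Study Design) gives it to both groups, the explicit trigger is item 9 of the three-month survey, and the listed one-month items never ask whether a dermatologist was seen.
- *That women who answer no to item 9 ought to have their records checked.* Leaving them unchecked fits the access limits in Sections 3.1 (Inclusion Criteria) and 13.2. Non-responders are ordinary attrition.
- *That biopsies by non-dermatologists need their own item.* The aims and Section 3.4 concern dermatology follow-up.
- *That the main comparison fails.* SSE performance is self-reported and does not use the EMR.

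**What to change.** - In Sections 3.1 (Study Design) and 3.3, replace 'anonymous' with 'confidential, coded by study number' at both time points.
- Send each woman a unique REDCap link tied to her study number and arm, say so in the protocol, and make the consent wording match.
- Add two sub-items to item 11: where the biopsy was done, and the diagnosis.
- Correct the EMR review paragraph so that it describes item 9 as asked: an appointment had, not made.
- Reconcile Sections 3.1 (Inclusion Criteria), 3.3, 3.4 and 13.2 on EMR trigger and scope, naming the survey and item, so that one trigger applies in both arms.
- Record for each biopsy and diagnosis whether it came from the EMR or from self-report.

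The cost is wording, two short sub-items in a survey meant to take under 2 minutes, and a check of the consent form. Women told that the survey is coded may answer slightly less freely, although they already consent to EMR access. No additional class of records needs to be opened.

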3.0 Procedures Involved

3.1 Study Design

Phase 1: *Delivery of educational SSE program.*

Each of the eight changing rooms of the Lynn Sage Comprehensive Breast of Northwestern Memorial Hospital will be equipped with a poster, brochures (Fig 1 and Fig 2) and cards with information about obtaining an appointment with a dermatologist for concerning skin lesions.

A woman research assistant will obtain consent to participate in the research and review of medical information, collect contact information and if the woman owns an iPhone X, 8+ or 8, and ensure receipt of an informational brochure. Women will be asked if they own an iPhone X, 8+ or 8 to assess the prevalence of these specific phones in the population of interest. These iPhones models are of particular interest to the research team as they offer superior image quality compared to older models. If a woman has this type of phone, she will be asked about her experience using it to take close-up pictures. The woman will be asked her preference for being contacted by email, telephone, or text message. The two arms of the study will be delivered on different weeks. During weeks 1,3,5 and 7 of the study period 400 women will be given brochures and a card with information on scheduling dermatology follow-up prior to check-out (Group 1), (Fig 3). During weeks 2, 4, 6 and 8 of the study period, 400 women will be given brochures to perform SSE at home and proceed to check-out of the mammogram area (Group 2). The women in Group 1 will also receive a reminder about performing a SSE one week after their mammogram visit via phone call,

Effect of SSE education delivered during the mammography experience.

email or text message. One month after the mammogram visit both groups will be called and surveyed to see if they checked their skin and/or made an appointment to see a dermatologist. Three months after the mammogram, both groups will be asked to participate in a complete survey (either via REDCap or telephone), including whether the women followed up in dermatology and if any concerning lesions were biopsied.

Fig 1. SSE Poster

[figure not shown]
[figure not shown]

Fig 2. Cover of SSE

[figure not shown]

Phase 2: Assessment of SEE Implementation

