14.0 Data Analysis

14.1. This convenience sample of women undergoing screening mammography will all receive education either as a brochure and a 1-week reminder or as only the brochure. Demographic characteristics of the two groups will be examined using means and standard deviations (age) and counts and percentages for all categorical variables. Primary outcomes of SSE performance, biopsy, and diagnoses will be compared using Chi-square tests of association or Fisher's exact tests where sample sizes were restrictive. Due to the skewed nature of the anxiety scale, a Wilcoxon rank sum test will be used to compare anxiety, the secondary outcome, in the two groups. Descriptive statistics will be performed for the tertiary outcome of dissemination.

15.0 Confidentiality and Data Management:

1. There are no biological specimens. All of the following data is collected in person consent and responses to structured interviews and focus groups.
2. Our systems are guarded against outside entry by Northwestern's own firewall supporting 128-bit encryption. This level of encryption provides the highest level of protection against hackers, computer break-ins, etc. All data is deidentified. Experienced research assistants will be employed and will receive training that includes emphasis upon the importance of confidentiality of information, and all personnel on the project will complete the required NIH training in the protection of human research participants.
3. Data will be retained in separate locked file cabinets and on computers with restricted and password protected access, without links to the master code list. All data based on the research will be reported in aggregate form. No individual respondents will be identified. Electronic data will be maintained in a study specific database on the server of the Department of Dermatology at the Feinberg School of Medicine. Paper-based files will be kept in a locked cabinet in a locked room within the Northwestern University Department of Dermatology research offices. Identifiable data will be kept separate from the case report forms and source documents. Data gathered as a result of this study are available to inspection on request by Food and Drug Administration or other government regulatory agency auditors, and the Northwestern University Institutional Review Board (IRB).

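### Prior skin self-examination, the natural baseline of the primary outcome, is listed only at 3 months and is not adjusted for in a comparison of arms set by alternate calendar week

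*Combined protocol and SAP*

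**What the plan says.** Section 3.1 (Study Design) sets allocation by calendar: "The two arms of the study will be delivered on different weeks". The intensive arm recruits in odd weeks ("During weeks 1,3,5 and 7 of the study period 400 women will be given brochures and a card") and the brochure-only arm in even weeks ("During weeks 2, 4, 6 and 8 of the study period, 400 women will be given brochures to perform SSE at home"). No randomisation between arms is described. Section 3.2 (Informed Consent, Participant Surveys, and Educational Intervention) says that staff will "acquire a randomly selected convenience sample of eligible participants (n=800"), and section 14.1 also calls the sample one of convenience.

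In section 3.3 (Research procedures and activities), items 1 to 3 of the 3-month survey ask about sunburn, indoor tanning and personal or family history of melanoma. Item 4 asks: "Have you ever performed a skin self-examination prior to your most recent mammogram". The Study Design section expects losses: "We anticipate a 20% attrition rate (Fig 3"). Women who do not complete the 3-month survey within 2 weeks are telephoned.

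Section 3.2 says that the survey offered around consent will cover melanoma knowledge and melanoma risk. Its eight listed items include none on risk factors or earlier SSE; the nearest is "Did you check your skin? (If no, please proceed to question #7").

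For analysis, section 14.1 promises a descriptive comparison ("Demographic characteristics of the two groups will be examined using means and standard deviations (age"), with counts for categorical variables, then chi-square or Fisher tests. Section 3.4 (Measures) also specifies a chi-square test for SSE, and tabulates risk factors by group.

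**The concern.** Whether a woman has examined her skin before is likely to be among the strongest predictors of whether she does so after the mammogram. With only four weeks per arm and no randomisation, the design does not protect balance on it, and an unadjusted test passes any imbalance straight into the primary result.

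The plan does collect the variable, but late. By 3 months the reminder may have changed what a Group 1 woman counts as an earlier self-examination, so the answer is partly a post-intervention measurement and a poor adjuster. It is also unavailable for women lost to follow-up, so the study cannot show whether they differed in prior SSE. Once enrolment closes, a clean baseline cannot be recovered.

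**Working it through.** **Where the variables are asked.** Comparing the three listed question sets:
- Enrolment (section 3.2, eight items plus demographics): no prior SSE, no risk-factor item.
- 1 month (section 3.3): neither.
- 3 months (section 3.3): risk factors in items 1 to 3, prior SSE in item 4.

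**Where they are used.** Risk factors are counted by group (section 3.4). Prior SSE is named in neither section 3.4 nor 14.1. The only regression is an intercept-only model for agreement between woman and dermatologist. No covariate or week term enters any comparison of arms.

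**The plan's own figures.** 400 + 400 = 800 enrolled. With 20% attrition, 400 × 0.80 = 320 responders per arm, and 0.20 × 800 = 160 women without 3-month answers. No SSE rate, effect size, alpha or power is given, so what follows is illustration.

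**Bias with no true effect.** Assume a two-sided 5% test and a 20 to 40 point gap in post-mammogram SSE between prior performers and others.
- Bias b = imbalance in prior SSE × gap.
- SE = √(2p(1−p)/320): 0.0395 at overall SSE rate p = 50%, 0.0377 at p = 35%.
- Rejection rate = Φ(b/SE − 1.96) + Φ(−b/SE − 1.96).

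| Imbalance | Bias (gap 20 / 40) | Rejection, p = 50% | Rejection, p = 35% |
|---|---|---|---|
| 5 points | 1 / 2 points | 5.7% / 8.0% | 5.8% / 8.3% |
| 10 points | 2 / 4 points | 8.0% / 17.3% | 8.3% / 18.5% |

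**How likely such imbalances are.** Assume 50% prevalence of prior SSE. Under individual allocation the SD of the imbalance is √(2 × 0.25/320) = 0.0395. Five points is then 1.3 SD (probability about 0.21) and ten points 2.5 SD (about 0.01). Under weekly allocation with about 80 responders a week, multiply the variance by 1 + 79 × ICC:
- ICC 0.02 (assumed): factor 2.58, SD 0.0635; ten points or more has probability about 0.12.
- ICC 0.05 (assumed): factor 4.95, SD 0.088; probability about 0.26.

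**Precision.** With 50% prevalence and p = 50%, the share of outcome variance explained by prior SSE is 0.25 × gap²/0.25 = gap², so 0.04 to 0.16. Adjustment is then worth 1/(1 − 0.04) = 1.04 to 1/(1 − 0.16) = 1.19 times the women, before any allowance for week.

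**The case against.** Several stronger readings are tempting, and the documents do not support them.

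- *All four items are contaminated by the intervention.* Sunburn, tanning and personal or family history are largely fixed. Late timing harms them mainly through non-response; the recall argument applies chiefly to prior SSE.
- *Risk is ignored until month 3.* Section 3.2 says the enrolment survey covers melanoma risk, and its open-ended items might draw out a risk factor. Section 3.4 tabulates risk factors by group, so imbalance among responders would be visible. What is missing is a listed baseline item and any adjustment.
- *The design's false-positive rate is 18% or more.* The rates above are conditional on an imbalance of the stated size. A 15-point imbalance would give 33 to 36% at a 40-point gap, but it is 3.8 SD under individual allocation. Chance imbalance under individual allocation is already inside the 5%. Larger imbalances become ordinary only with week-level clustering, for which the documents give no figure.
- *The enrolment items on checking skin and making an appointment are misplaced and should be replaced.* Their retrospective wording, and the use of the same term for the 3-month survey in section 3.1, leave it unclear when they are asked.

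Two further points are fair. The telephone fallback reduces non-response. Prior and post-mammogram SSE are also on the same 3-month form, so the covariate is missing mainly where the 3-month outcome is missing. The loss is therefore less in an adjusted 3-month analysis than in describing dropouts, and in women who report SSE at 1 month only.

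None of this answers the core: prior SSE is asked after an arm-specific reminder and is then left out of the comparison.

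**Conclusion.** The point holds for prior SSE and more weakly for the risk factors. Allocation by alternate week, a baseline first listed after the intervention and an unadjusted test together leave the primary SSE result open to an imbalance that the plan can neither measure cleanly nor correct. The size is not known. On the stated assumptions, a modest imbalance costs 1 to 2 points and lifts the error rate slightly, while a 10-point imbalance costs 2 to 4 points and takes it to between 8.0% and 18.5%. The change is worth making because it is cheap and cannot be made after enrolment. It improves a weakly protected comparison; it does not turn alternate weeks into randomisation.

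**What to change.** 1. Ask prior SSE and the three risk-factor items of every woman at enrolment, before the 1-week reminder and ideally before the brochure is discussed. Posters and brochures are in the changing rooms, so this is not fully before exposure, but it precedes the reminder. Keep the risk items at 3 months as well if perceived risk is wanted as a follow-up measure.
2. Link enrolment answers to follow-up by study number, and reconcile this with the description of the REDCap surveys as anonymous. The medical-record review triggered by item 9 already needs linkage.
3. In section 14.1, make the primary SSE comparison a logistic regression on arm adjusted for prior SSE, risk factors and age, reported as a standardised risk difference. Standard errors should account for week, with a small-sample correction for four weeks per arm. Keep the chi-square test as support.
4. State that adjustment does not remove unmeasured week-level differences.

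The cost is four existing yes/no questions at an interview already planned and a little more analysis. Asking about SSE at enrolment is a mild prompt. It falls equally on both arms but could slightly shrink the contrast between them. Allowing for week may widen the confidence interval.

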3.1 Inclusion Criteria for Patient

Women 18 years of age and older, who are waiting to have a mammogram

Women agree to complete informed consent and registration forms allowing follow-up reminders and access to their EMR record limited to the visit with a dermatologist or primary care physician regarding a concerning skin lesion and the results of the biopsy of the lesion.

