3.4 Measures

The number of women with risk factors for melanoma, who performed SSE after the screening mammogram, who found a concerning mole, who saw dermatology, who had a concerning lesion biopsied in each group will be analyzed by descriptive statistics. The difference in proportions of women who 1) performed SSE 2) saw a dermatologist in the educational intervention group from the intensive intervention group will be compared using a χ^2 test. If the woman responded “yes” to follow-up in dermatology, a chart review of the electronic medical record will be performed to assess whether any lesions were biopsied and pathology of the concerning lesions. The accuracy of the woman’s selection of a concerning lesion will be assessed by examining the correspondence rate between the woman’s assessment during SSE and the dermatologist. The overall correspondence rate will be calculated with a random intercept-only mixed logistic regression model. The statistical analysis will be performed by [name], MPH.

Online data

REDCap survey (see page 8 above)

Approvals required

Effect of SSE education delivered during the mammography experience.

[name] obtained permission for this research to be conducted in the Lynn Sage Comprehensive Breast Center of Northwestern Medicine/Prentice Women's Hospital

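### The 3-month survey dates skin self-examination from the woman's latest mammogram, but the outcome is counted from the study mammogram, so some women who have another mammogram in between could be misrecorded

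*Combined protocol and SAP*

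**What the plan says.** Section 3.3 Research procedures and activities sets the timing: "3 months after the mammogram, an anonymous REDCap survey will be emailed to each woman enrolled in both groups". Women who have not responded after 2 weeks are surveyed by telephone. Two items of that survey divide SSE in time:

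- Item 4 (prior behaviour): "Have you ever performed a skin self-examination prior to your most recent mammogram".
- Item 5 (behaviour after the intervention): "Did you perform a skin self-examination after your most recent mammogram". A negative answer carries the instruction "If no, then go to item 8", which passes over items 6 and 7 (whether a concerning mole was found, and whether an appointment was made for it).

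Section 3.4 Measures counts women "who performed SSE after the screening mammogram". Section 14.0 Data Analysis makes SSE performance a primary outcome: "Primary outcomes of SSE performance, biopsy, and diagnoses will be compared using Chi-square tests of association", with Fisher's exact test as the alternative.

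The 1-month survey, also in section 3.3, asks about SSE without naming any mammogram: "Did you check your skin? (If no, please proceed to question #4". Sections 3.1 Study Design and Phase 2 give that survey to both groups, whereas the procedure in section 3.3 names only group 1.

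Eligibility (3.1 Inclusion Criteria for Patient) is "Women 18 years of age and older, who are waiting to have a mammogram". The documents neither mention nor exclude a further mammogram during follow-up.

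**The concern.** The survey item and the outcome definition use different reference points. The definition is fixed at the study visit. The item moves with the woman's imaging history, and nothing in the items tells her to answer for the visit at which she enrolled.

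A woman who examined her skin because of the brochure or reminder, and then had another mammogram, can truthfully place that examination before her latest mammogram. A success on a primary outcome would then be recorded as a failure, and the prior-SSE item would be overstated. The skip would also drop her answers on a concerning mole. Item 8 is addressed to women who did not examine themselves. If she reports an appointment there, it falls on the no-SSE side of the study's second aim.

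**Working it through.** **Wording check.** Consider a woman whose study mammogram is at time 0 and who has a second mammogram before she answers.

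| When she did SSE | Item 4 | Item 5 (literal answer) | Outcome under 3.4 Measures | Agreement |
|---|---|---|---|---|
| Only between the two mammograms | Yes | No | Yes | No |
| Between them and again after the second | Yes | Yes | Yes | Yes on outcome; prior SSE overstated unless she had also done SSE before time 0 |
| Only after the second | No | Yes | Yes | Yes |

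Only the first row loses the outcome, and only if she answers literally. In that row items 6 and 7 are skipped. Items 8 to 11 are still asked, and the EMR review depends on item 9, so it is still reached.

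**Size.** The plan states no SSE rate, effect size, alpha, power or repeat-mammogram rate, so there is no figure to reproduce. The inputs are:

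- From the documents: 400 women per group and 20% anticipated attrition, so 400 × 0.8 = 320 responders per arm and 640 in all.
- Assumed: true SSE s of 50% in Group 1 and 40% in Group 2; a share r of 5-15% with another mammogram within 3 months; a share q of the SSE performers among them who checked only before it; everyone answers literally; two-sided alpha 0.05.

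Recorded rate = s × (1 − r × q). Misdated women per arm = 320 × s × r × q.

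With q = 0.5 in both arms:

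- r = 5%: misdated 320 × 0.50 × 0.05 × 0.5 = 4.0 and 320 × 0.40 × 0.05 × 0.5 = 3.2, total 7.2. Difference 10 × (1 − 0.025) = 9.75 points.
- r = 15%: misdated 12.0 + 9.6 = 21.6. Difference 10 × (1 − 0.075) = 9.25 points.

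Power is 72.1% with no misdating, 70.1% at r = 5% and 66.1% at r = 15%.

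Varying q as well, still equal in both arms:

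- Mildest case (r = 5%, q = 25%): 2.0 + 1.6 = 3.6 women, 9.9 points, power 71.1%.
- Most severe case (r = 15%, q = 100%): 24.0 + 19.2 = 43.2 women, 8.5 points, power 60.0%.

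**Timing that differs by arm.** Only Group 1 gets the 1-week reminder, so q may differ between arms:

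| q in Group 1 / Group 2 | Recorded difference, true 50% v 40%, r = 5% to 15% | Recorded difference, true 50% v 50%, r = 5% to 15% |
|---|---|---|
| 0.25 / 0.75 | 10.9 to 12.6 points | +1.25 to +3.75 points |
| 0.75 / 0.25 | 8.6 to 5.9 points | −1.25 to −3.75 points |

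For example, with 0.75 / 0.25 and r = 15%: 0.50 × (1 − 0.1125) − 0.40 × (1 − 0.0375) = 0.44375 − 0.385 = 0.05875. The direction follows from which arm has the larger q, and the documents do not determine that.

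**The case against.** Four points weigh against the concern.

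1. **Few women may be affected.** Three conditions must hold together: a further mammogram before the survey, SSE only before it, and a literal answer. Some women will answer for the study visit anyway. The posters and brochures are in the changing rooms, so a return to the same centre could itself prompt an SSE that item 5 counts. This stands. A reader might infer that every woman called back is misrecorded, but the items do not have that effect.
2. **SSE is also asked at 1 month.** The question has no mammogram anchor and could capture an early SSE. This stands in part. No rule combines the two surveys or says which one defines the outcome. Both may be anonymous, so linking them is not assured, and section 3.3 names only group 1 for the 1-month contact.
3. **Later data survive.** A reader might infer that biopsy and diagnosis, the other primary outcomes, are lost as well. They are not lost through this skip, because items 9 to 11 and the EMR review are still reached.
4. **The effect on the arm comparison is uncertain.** It is tempting to infer that the reminder brings Group 1's SSE forward and so costs Group 1 more successes. That needs a timing for the second mammogram, which the documents do not give. If it falls in the first week, SSE prompted by the reminder comes after it and counts. Group 2 has the brochure from the visit and may check at once.

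The survey's introductory text is not shown in the documents, so it might already direct women to the study visit.

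**Conclusion.** The mismatch between items 4 and 5 and the outcome in section 3.4 is clear from the text, and no stated rule would repair it once the data are in. It harms the outcome only for women who meet all three conditions.

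Under the equal-timing assumptions with q = 0.5, about 7 to 22 of 640 women (1.1% to 3.4%) are misdated, and an assumed 10-point difference is recorded as 9.8 to 9.3 points. If timing differs by arm, the recorded difference can be too large or too small. Every rate here is an assumption, and because all such women are taken to answer literally, the figures lean towards overstating the loss for a given r and q. The severity is minor. The change is worth making because it aligns a primary-outcome item with its own definition at almost no cost.

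**What to change.** In items 4 and 5, replace the reference to the most recent mammogram with a fixed anchor that needs no personal link, such as *the mammogram visit when you joined this study*. Use the same wording in the online and telephone versions, and have items 6 to 9 refer to the time since that visit.

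The cost is rewording only. An individual enrolment date filled in for each woman would be more precise, but it requires a form linked to the person, and the 3-month survey is described as anonymous. It should be used only if the survey is not in fact anonymous.
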